###### **4.1.5 Pharmacokinetic-Evaluable Population**

The pharmacokinetic-evaluable patient (PKEP) or PK population comprises all patients in the ITT population who have at least one post-dose drug concentration measurement at a scheduled visit timepoint. Patients may be excluded from the PKEP population if they significantly violate the inclusion or exclusion criteria or deviate significantly from the protocol, or if data are unavailable or incomplete which may influence the PK analysis, such as the absence of properly documented date and time for the baloxavir marboxil administration and PK sample collection.

Decisions on exclusion from the PKEP population may be made prior to database closure by the clinical pharmacologist. Excluded patients will be documented, together with the reason for exclusion.

#### **4.1.6 Sparse Pharmacokinetic-Evaluable Population**

The sparse PKEP or sparse PK population comprises all patients in the PK population who did not provided informed consent to intensive PK sampling.

#### **4.1.7 Extensive Pharmacokinetic-Evaluable Population**

The extensive PK population comprises all patients in the PK population who provided informed consent to intensive PK sampling.

#### **4.1.8 Safety Population**

The safety-evaluable patient population comprises all patients who received at least one dose of treatment regardless of whether they have any follow-up assessments. Patients will be classified according to treatment actually received.

### **4.2 ANALYSIS OF STUDY CONDUCT**

The number of patients who enroll, discontinue, or complete the study will be summarized by treatment arm. Reasons for premature study withdrawal will be listed and summarized by treatment arm. Major protocol deviations will be listed and evaluated for their potential effects on the interpretation of study results.

### **4.3 ANALYSIS OF TREATMENT GROUP COMPARABILITY**

Demographic and baseline characteristics (including age, sex, race/ethnicity, height, weight, BMI and vaccination status) will be summarized using means, standard deviations, medians, and ranges for continuous variables and proportions for categorical variables, as appropriate. Summaries will be presented overall and by treatment received for the safety population. If it is found that there is a large difference in the number of patients in the safety population compared to the ITTi population, additional summaries will be produced based on randomized treatment.

Medical history data, including surgery and procedures and baseline conditions, will be summarized descriptively by treatment group using the safety population. Descriptive summaries of any previous and concomitant treatment will be produced by treatment group.

## 4.4 Visit Windows

**Table 2 Acceptable Time Windows for Parameters Other Than Data from the Patient Diary**

Time Point (Scheduled Time Point)	Acceptable Time Window
Pre-dose at Visit 1 (Day 1)	Before dosing on Day 1
Post-dose at Visit 1 (Day 1)	Between 0.5 and 4 hours after dosing (on Day 1)
Visit 2 (Day 2)	Day 2
Optional Visit 1 (Day 3)	Day 3
Visit 3 (Day 4)	Day 4
Visit 4 (Day 6)	Between Day 5 and Day 7 as follows: -if patient presents on Day 5 with no Day 4, and no Day 6 this will be classed as Visit 4 -if patient presents on Day 5 with no Day 4, and Day 6 this will be classed as Visit 3. -if patient presents on Day 5 with Day 4 and no Day 6 this will be classed as Visit 4.
Visit 5 (Day 10)	Between Day 8 and Day 12
Optional Visit2 (Day 15)	Between Day 13 and Day 22
Visit 6 (Day 29)	On or after Day 23
Withdrawal	Date of withdrawal + 14 days

\* if time is missing for data collected on Visit 1 where, per the schedule of activities, this data should be collected at 'v1 screening' or 'v1 post-dose' it is defined as 'Pre-dose at Visit 1 (Day 1)' or 'Post-dose at Visit 1 (Day 1)' respectively.

Measurements collected within the acceptable time window for each scheduled assessment time point, including data obtained at the time of withdrawal, will be used for the analyses of all endpoints at each assessment time point. For all patients with multiple values within a visit window, the value obtained closest to the target time point will be used. If two measurements collected with the same time deviation exist before and after the target time point, the measurement obtained before the target time point will be adopted for analysis. The assessment time point having no measurements within the corresponding acceptable time window will be considered as missing.

In the assessment of data from sources other than the patient diary, if there are multiple values which may be adopted for a scheduled assessment time point (even though the above rules have been strictly followed), the measurements at the time point entered in the Case Report Form (CRF) will be adopted.

For summaries of data not collected by visit, such as adverse events, medical history and concomitant medications, all data up to the last exposure date will be included.

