## Appendix 1 Schedule of Activities

Day(s)	Treatment Period						Follow-Up Period				
	D1		D2	D3	D4	D5	D6	D7-9	D10	D15	D29 or ET
Visits	V1 Screening	V1 Post-dose	V2	OpV1 a	V3		V4		V5	OpV2 a	V6
Visit Window (days)					+1		±1		±2	±3	±3
Written informed consent/assent	x										
Inclusion/exclusion criteria	x										
Demographics	x										
Medical history b	x										
Randomization	x										
Study drug administration c		x	x	x	x	x					
Patient diary:											
Body temperature measurement d	Four times daily				Twice daily			Once daily			
Assessment of influenza symptoms e	Twice daily							Once daily			
Physical examination	x f		x f	(x) f	x f		x		x	(x g )	x f
Vital signs measurement	x		x	(x)	x		x		x	(x g )	x h
Adverse event assessment		x	x	(x)	x		x		x	(x g )	x
Concomitant therapies assessment	x		x	(x)	x		x		x	(x g )	x
Interview for meal consumption	x	x									
Clinical laboratory tests		x					x			(x g )	(x g )
Nasal/nasopharyngeal swabs (virology test) i	x		x		x		x		x	(x g )	(x g )

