#### **4.5.4 Vital Signs**

For each of the vital signs (diastolic blood pressures, systolic blood pressures, respiratory rate and pulse rate), summary statistics of observation and the change from baseline will be presented by treatment group for each scheduled time point.

Baseline is defined as the last assessment prior to treatment.

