#### **4.6 EFFICACY ANALYSIS**

The statistical analyses of efficacy endpoints will be descriptive. The ITTi population will be used for all analyses. Additional analysis of efficacy analysis presenting the ITT population will not be completed.

The data will be summarized using means, standard deviations, medians, and ranges for continuous variables and proportions for categorical variables, as appropriate. Time-to-event endpoints and duration endpoints will be summarized using Kaplan-Meier plots and summaries of the median survival time. Summaries will be presented by treatment group.

Efficacy endpoints are based on the CARIFS questionnaire data which is recorded by parent/ caregiver using handheld device. This assessment data should be recorded for the following time periods:

Period	Time
Morning	0.500-10.59
Noon	11.00-14.59
Evening	15.00-18.59
Bedtime	19.00-23.59

\*data should not be recorded between 00.00 and 4.59.

In the case where the recorded time of an assessment is outside the period time window for that assessment, the end time of the period should be imputed as the assessment time.

In the case where the assessment time falls into the period between 00.00 and 4.59 (due to technical error) the assessment date will be imputed to the date prior to recorded assessment date and the assessment time will be imputed to the end time of the period time window.

The imputation method used in the derivation of time to alleviation of influenza signs and symptoms is described in Section 4.6.1. No further imputation methods will be used.

In all time to event analysis, patients who withdraw prior to event of interest will be censored at the last observation timepoint.

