### **Proportion of patients with positive influenza virus titer at each timepoint**

Proportion of patients positive for influenza virus titer will be presented by treatment at each visit and is defined as the percentage of patients whose influenza virus titer is not less than the lower limit of quantification ( $0.75 \log_{10} \text{TCID}_{50}/\text{mL}$ ) or positive among those assessed for influenza virus titer on Days 2, 4, 6, and 10.

Patients with a positive influenza virus titer on Day 1 will be included in this analysis.

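### Read in calendar days, SAP Table 2 leaves Visit 3 missing for a child seen within window on Day 5 (Visit 3) and Day 7 (Visit 4)

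*SAP*

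**What the plan says.** Protocol Appendix 1, repeated in SAP Appendix 2, gives Visit 3 (Day 4) a window of +1 day and Visit 4 (Day 6) a window of ±1 day.

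SAP Section 4.4, Table 2, sets the analysis windows for everything except diary data. The Visit 3 window is Day 4 alone. The Visit 4 window is Days 5 to 7, with three rules for a Day 5 attendance:

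- Rule 1: "if patient presents on Day 5 with no Day 4, and no Day 6 this will be classed as Visit 4".
- Rule 2: "if patient presents on Day 5 with no Day 4, and Day 6 this will be classed as Visit 3".
- Rule 3: Day 5 with Day 4 attended and Day 6 not attended is Visit 4.

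The text below the table adds that the value closest to the target is used. When two values are equally far from it on either side, "the measurement obtained before the target time point will be adopted for analysis". For an empty window, "The assessment time point having no measurements within the corresponding acceptable time window will be considered as missing". If several values still compete after these rules, the time point entered in the CRF decides.

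**The concern.** Rule 2 is the only route from Day 5 to Visit 3, and it requires attendance on Day 6. None of the three rules mentions Day 7, although Day 7 is a valid Visit 4 day in both the schedule and the Visit 4 row of Table 2. A child who comes one day late to each visit, within both windows, therefore falls under rule 1 if the rules are read in calendar days.

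An in-window Visit 3 measurement would then be absent from the Day 4 summary, and the Day 6 summary might carry the Visit 3 measurement in place of the Visit 4 one. Swabs and vital signs are scheduled at both visits. Vital signs are among the primary safety endpoints (SAP Section 2.2.1), and SAP Section 4.5.4 says that "summary statistics of observation and the change from baseline will be presented by treatment group for each scheduled time point". The virology summaries in SAP Section 4.6.2 are by visit; the titer proportion, for example, is taken "among those assessed for influenza virus titer on Days 2, 4, 6, and 10".

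**Working it through.** The plan gives no figure to reproduce here. The check applies the Table 2 rules to each possible attendance.

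**Step 1: compliant pairs.** Visit 3 can fall on Day 4 or 5, and Visit 4 on Day 5, 6 or 7. That is 2 × 3 = 6 combinations. Removing the one that puts both visits on Day 5 leaves 5.

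**Step 2: apply Table 2 in calendar days**, counting distance from target in whole days.

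| Days attended (Visit 3, Visit 4) | Rule for Day 5 | Day analysed as Visit 3 | Day analysed as Visit 4 |
|---|---|---|---|
| 4, 5 | Rule 3 | 4 | 5 |
| 4, 6 | none needed | 4 | 6 |
| 4, 7 | none needed | 4 | 7 |
| 5, 6 | Rule 2 | 5 | 6 |
| 5, 7 | Rule 1 | missing | 5 |

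In the last row, Days 5 and 7 are both in the Visit 4 window. The distances from Day 6 are |5 − 6| = 1 and |7 − 6| = 1, so the tie rule keeps Day 5 and Day 7 goes unused. If distance is counted in hours, either value may be closer and be kept. In both cases Visit 3 is empty and exactly one of the two measurements is unused.

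**Step 3: the CRF fallback.** It operates only when several values still compete for one time point. On a whole-day count the tie rule has already settled Visit 4. Even if the fallback were triggered, it would choose between values for Visit 4 and could not fill Visit 3.

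**Step 4: does naming Day 7 disturb anything else?** Days 4 to 7 give 2⁴ − 1 = 15 non-empty attendance patterns, of which 8 include Day 5. Rules 1 and 2 apply only where Day 5 was attended and Day 4 was not, which is 4 patterns; the other 11 cannot change. The four, written as (Visit 3, Visit 4), are:

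- Day 5 alone: (missing, 5) before and after.
- Days 5 and 6: (5, 6) before and after.
- Days 5, 6 and 7: (5, 6) before and after, since Day 6 is on target.
- Days 5 and 7: (missing, 5) before, (5, 7) after.

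So 14 of the 15 patterns are unchanged, and the one that changes is then mapped as attended.

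**Step 5: which analyses.** By-visit vital signs and the by-visit virology summaries at Days 4 and 6 use these windows directly. Section 4.4 also applies windowed values to all endpoints at each assessment time point. Virology AUC and time to cessation of shedding (Section 4.6.2) and PK tabulated by timepoint (Section 4.7) may therefore be touched, but the SAP does not say whether they use windowed values. Diary endpoints are outside Table 2, and adverse events are not collected by visit. Routine laboratory tests are scheduled at Visit 4 but not Visit 3, so a sample taken on Day 7 alone would still be used.

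**The case against.** The strongest objection is that Day 4 and Day 6 are also the table's names for the visits: its rows are labelled Visit 3 (Day 4) and Visit 4 (Day 6), and the virology sections speak of Days 2, 4, 6 and 10 although visits may fall on neighbouring days. If no Day 6 means no Visit 4 attendance, a child seen on Days 5 and 7 falls under rule 2 and is mapped correctly. This stands as a possible reading. A reader might infer that compliant children will certainly be misassigned; the documents do not support that without the calendar-day reading. Against the visit-label reading, the same row gives its window as Days 5 to 7 and speaks of presenting on Day 5, both calendar days, and nothing in the table signals a switch. A programmer could reasonably code either.

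Second, an analysis window may be narrower than a scheduling window, and Day 5 is as far from Day 4 as from Day 6. Keeping a Day 5 value out of the Day 4 summary is not in itself an error. That is fair, but rule 2 already accepts Day 5 as Visit 3 when a later attendance fills Visit 4, and the SAP gives no reason to treat Day 7 differently from Day 6. The unused second measurement is a loss in any case.

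Third, one failing pair in five might be taken as a rate. It is a count of combinations, not of children, and the documents give no attendance frequencies.

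**Conclusion.** The point holds as a minor one, conditional on reading Table 2 in calendar days. On that reading, one of the five compliant pairs, Days 5 and 7, leaves Visit 3 missing and one valid measurement unused. That Day 5 is the value kept rests further on counting distance in whole days.

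No patient count or size of effect can be given, because the documents do not say how often this pattern would occur. It would also go too far to say that the effect is confined to by-visit vital signs and virology, since the SAP leaves open whether AUC, time to cessation of shedding and by-timepoint PK use windowed values. Nor do the documents support inferring a bias between arms or a changed conclusion: nothing in them ties the pattern to treatment, "The statistical analyses of efficacy endpoints will be descriptive", Protocol Section 6 says the same of safety and pharmacokinetics, and no test depends on the rule.

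**What to change.** In SAP Table 2, reword the first two Day 5 rules and leave the third as it is:

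- Rule 1: *Day 5 with no Day 4, and no Day 6 or Day 7, is classed as Visit 4.*
- Rule 2: *Day 5 with no Day 4, and a further visit on Day 6 or Day 7, is classed as Visit 3.*

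This gives the right mapping for Days 5 and 7 whichever meaning of Day 6 was intended, and it keeps the existing treatment of a lone Day 5 attendance as Visit 4. The cost is two phrases in the table and the matching line of windowing code, with no new data collection.

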### **3. STUDY DESIGN**

#### **3.1 DESCRIPTION OF THE STUDY**

This is a multicenter, randomized, double-blind, active-controlled (i.e., oseltamivir) study to assess the safety, pharmacokinetics, and efficacy of baloxavir marboxil compared with oseltamivir in pediatric patients 1 to < 12 years of age with influenza-like symptoms.

This study is designed to enroll approximately 120 otherwise healthy male and female pediatric patients with influenza-like symptoms presenting within 48 hours of symptom onset.

Patients will be recruited in parallel to the following two cohorts:

- 5 to < 12 years of age (minimum 40 patients)
- 1 to < 5 years of age (minimum 20 patients)

Baloxavir marboxil will be given as a single-dose, based on body weight at screening. The approved dose for oseltamivir in pediatric patients 1 to 12 years of age is BID for 5 days, based on body weight (see Section 4.3.2.2). Either drug, along with the corresponding placebo of its comparator in this trial, will be started at the time of randomization.

Patients will be screened and randomized on Day 1 and assigned in a 2:1 ratio to receive a single oral dose of baloxavir marboxil based on body weight (2 mg/kg for patients weighing < 20 kg or 40 mg for patients weighing  $\geq$  20 kg) or oseltamivir (dose based on body weight) for 5 days. Re-screening of patients who fail to meet the inclusion and exclusion criteria will not be permitted for the same illness episode, as the time from symptom onset to treatment window is limited to 48 hours.

The study consists of two periods: a 5-day treatment period (mandatory visits on Days 1, 2, and 4) and a 24-day safety follow-up period (mandatory visits on Days 6, 10, and 29). Therefore, the total study duration for each patient will be 29 days.

During the 5-day treatment period, each patient randomized to baloxavir marboxil will receive the oseltamivir matching placebo BID for 5 days, and those patients randomized to oseltamivir will receive one dose of baloxavir marboxil matching placebo on Day 1.

[figure not shown]
The following assessments will be conducted at clinic visits: physical examination, vital signs, adverse events, concomitant therapies, clinical laboratory tests, and nasal/throat swabs. Please see [Appendix 1](#) for details concerning the timing of these assessments. In addition, pharmacokinetic (PK) samples will be collected at the timepoints indicated in [Appendix 2](#).

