## 2.4 ANALYSIS TIMING

The primary study analysis will occur when the last patient has either withdrawn or completed his or her Day 29 visit, and will be based on all available data for all patients up to and inclusive of their Day 29 assessment date, as well as safety follow-up data for patients that withdrew prior to Day 29.

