## **4.5 SAFETY ANALYSES**

### **Safety Endpoints (Primary Objective)**

The primary objective for this study is to compare the safety of a single dose of baloxavir marboxil with 5 days of oseltamivir administered twice daily. The safety population will be used for all safety analyses. Patients will be analyzed according to the treatment they actually received.

The safety of baloxavir marboxil will be evaluated for adverse events, vital signs measurements, and clinical laboratory tests. Safety parameters will be summarized or listed for the safety population.

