#### **4.5.1 Adverse Events**

AEs will be classified by system organ class (SOC) and preferred term using Medical Dictionary for Regulatory Activities (MedDRA) Version 22.0 and adverse event severity will be graded according to National Cancer Institute Common Terminology Criteria for Adverse Events (NCI CTCAE) v5.0 or the Adverse Event Severity Grading Scale for events not specifically listed in NCI CTCAE toxicity grading scale ([Table 2](#) of the protocol) on the eCRF, AEs reported after the initial dose of the study drug will be used for safety analyses.

In summaries by SOC and preferred term (PT), AEs will be sorted by overall decreasing frequency within each SOC and PT.

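### SAP 4.4 ends adverse-event and concomitant-medication summaries at an undefined last exposure date, which contradicts SAP 2.4 and, read literally, drops almost all of the safety follow-up

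*SAP*

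**What the plan says.** The sentence follows Table 2 in SAP 4.4 (Visit Windows). It concerns information that is not tied to a visit, and its rule reads: "such as adverse events, medical history and concomitant medications, all data up to the last exposure date will be included". The term *last exposure date* appears nowhere else in the SAP or the protocol and has no definition.

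Other parts of the plan set different limits:

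- **SAP 2.4 (Analysis Timing).** The primary study analysis "will be based on all available data for all patients up to and inclusive of their Day 29 assessment date". The same sentence adds the safety follow-up of anyone who left the study early.
- **SAP 4.5.1 (Adverse Events).** "AEs reported after the initial dose of the study drug will be used for safety analyses". The treatment-emergent definition that follows depends on the start of treatment and has no upper limit.
- **Protocol 3.1.** After a 5-day treatment period there is "a 24-day safety follow-up period (mandatory visits on Days 6, 10, and 29". On dosing, "each patient randomized to baloxavir marboxil will receive the oseltamivir matching placebo BID for 5 days".
- **Protocol 5.3.1 and 4.4.** Adverse events are collected until 28 days after the last dose, and concomitant therapy until the completion or discontinuation visit. These are collection rules, not analysis windows.

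**The concern.** SAP 4.5 states: "The primary objective for this study is to compare the safety of a single dose of baloxavir marboxil with 5 days of oseltamivir". The adverse-event tables are a main part of that comparison. SAP 4.4 is the only text that gives those tables an end date, and the date it gives is tied to dosing rather than to follow-up. A programmer who follows it would leave out of the tables most of the period that the protocol sets aside for safety follow-up. A programmer who follows SAP 2.4 would include it. The SAP does not say which rule prevails, so the content of a primary-objective table depends on a choice made at programming.

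Laboratory findings show the practical effect. Protocol Appendix 1 requires laboratory tests at Day 1 post-dose and Day 6, and SAP 4.5.3 treats the Day 1 sample as baseline. An adverse event detected by, and dated to, the Day 6 sample would fall outside a Day 5 cut, even though the laboratory table would still show the abnormal value.

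**Working it through.** **Inputs**

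- Treatment period of 5 days, safety follow-up of 24 days, total of 29 days (Protocol 3.1).
- Ten twice-daily doses of oseltamivir or its placebo. If the first dose is before 16:00, the tenth is on the evening of Day 5. If it is after 16:00, the tenth is on the morning of Day 6 (Protocol 4.3.2.2).
- Mandatory adverse-event assessments at Day 1 post-dose and Days 2, 4, 6, 10 and 29, six in all (Protocol Appendix 1).
- Visit 6 at Day 29 ± 3 (Protocol Appendix 1).
- Adverse-event collection to 28 days after the last dose (Protocol 5.3.1).

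**Step 1: the plan's own figures.** 5 + 24 = 29, and Days 6 to 29 are 24 days, as stated. The detection table (SAP Table 1) also reproduces. With 1 − (1 − p)^80, incidences of 1% to 5% give 55.2%, 80.1%, 91.3%, 96.2% and 98.3%.

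**Step 2: the last dosing day.**

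- Start before 16:00: two doses on each of Days 1 to 5 make 10, so the last dose is on Day 5.
- Start after 16:00: one dose on Day 1, two on each of Days 2 to 5 (8) and one on Day 6 make 10, so the last dose is on Day 6.

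Both arms take a twice-daily product, so the dates are the same in both arms if placebo counts as exposure.

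**Step 3: what a literal cut leaves out.**

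| Cut | Study days left out | Follow-up days left out | Mandatory assessments after the cut |
|---|---|---|---|
| Day 5 | 24/29 = 82.8% | 24 of 24 | 3 of 6 (Days 6, 10, 29) |
| Day 6 | 23/29 = 79.3% | 23 of 24 | 2 of 6 (Days 10, 29) |
| Day 29 (SAP 2.4) | 0 | 0 | 0 |

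**Step 4: an alternative reading, by inference only.** SAP 4.5.6 sets exposure at 1 day for baloxavir and counts first to final dose for oseltamivir. If that defined the cut, baloxavir would stop at Day 1 (28/29 = 96.6% of days left out) and oseltamivir at Day 5 or 6. The windows would be unequal in baloxavir's favour. SAP 4.5.6 defines a duration for the exposure table and does not say that it governs adverse-event windows.

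**Step 5: effect on detection, as an illustration.** The documents give no onset timing, so the fraction of events starting before the cut is assumed. For a 3% event among 80 patients, the chance of seeing at least one case is 1 − (1 − 0.03f)^80:

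- f = 1: 91.3%
- f = 0.75: 83.8%
- f = 0.50: 70.2%
- f = 5/29 (uniform onset, Day 5 cut): 34.0%

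**Step 6: the end of follow-up.** The collection period ends on Day 5 + 28 = 33 or Day 6 + 28 = 34. Visit 6 falls between Day 26 and Day 32. Collection therefore ends 1 to 8 days after the last visit (33 − 32 to 34 − 26), and 4 or 5 days after a visit on Day 29. A Day 29 data cut does not settle these days either.

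**The case against.** The strongest reply is that the sentence is a slip that nobody would follow. It is a general closing line under visit windows and it includes medical history, for which a last-exposure cut has little meaning. Table 2 above it runs to Visit 6 and to 14 days after withdrawal. SAP 2.4 and 4.5.1 both point to full follow-up. The sentence also says that data up to the date are included, and does not say in words that later data are excluded.

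It may be a slip, but the SAP does not say so. If later data are included anyway, the sentence has no function and should be removed. As the more specific statement about these summaries, it could reasonably be followed.

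Several narrower points stand:

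- The conflict with SAP 4.5.1 is less direct than the one with SAP 2.4, because 4.5.1 gives no end date rather than a different one.
- The unequal-window reading in Step 4 is an inference, and the conclusion does not depend on it.
- The visit counts overstate the loss. The Day 6 visit also picks up events that began on Days 4 and 5, and those would still count under a Day 5 cut.
- No number of lost events can be derived from the documents.
- The Day 33/34 figures assume that the placebo doses count as study drug. Counted from the single baloxavir dose, Day 1 + 28 is Day 29.

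The reach is also limited. Adverse-event collection, monitoring-committee review and the analysis of deaths (SAP 4.8) are untouched, as are the laboratory and vital-sign tables, which are built by scheduled time point (SAP 4.5.3, 4.5.4). All analyses are descriptive.

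**Conclusion.** The concern holds. SAP 4.4 sets an undefined end date that directly conflicts with SAP 2.4 and does not fit the open-ended rule in SAP 4.5.1. Applied literally, with placebo doses counted as exposure, it leaves 24 or 23 of the 24 safety follow-up days out of the adverse-event and concomitant-medication summaries. These figures assume the full ten-dose schedule and are shares of time and visits, not of events.

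Two secondary efficacy summaries may also be affected, but only by inference. Influenza-related complications come from the adverse-event pages but have their own after-treatment wording, and antibiotic use names no data source (both SAP 4.6.1).

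This is a stated rule that would give a wrong primary-objective table if followed, so it must be fixed.

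**What to change.** - In SAP 4.4, delete the last-exposure cut-off and state one window on the same basis in both arms, whether the product taken is active or placebo.
- Summarise all treatment-emergent adverse events, as defined in SAP 4.5.1, through the end of study follow-up, including safety follow-up after withdrawal.
- Summarise concomitant medications through the completion or discontinuation visit, to match Protocol 4.4.
- State that complications and antibiotic use follow the same windows.
- In SAP 2.4, reconcile the Day 29 data cut with the collection period in Protocol 5.3.1, and say how adverse events reported after the Day 29 visit are handled, identically in both arms.

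The cost is one replaced sentence in SAP 4.4, a line for complications and antibiotics, a reconciling phrase in SAP 2.4 and a changed date filter in the programs. No new data are needed.
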